3.5 Safety Endpoints

- Frequencies of treatment-emergent adverse events (TEAEs), treatment-emergent serious AEs (TESAEs), treatment-related TEAEs (unlikely related, probably related, and possibly related), TEAEs leading to treatment discontinuation or trial withdrawal, and deaths during the trial for MC2-25 cream compared to MC2-25 vehicle.

- Mean change in vital signs (heart rate (HR), systolic blood pressure (SBP), diastolic blood pressure (DBP), and body temperature (temp)) from Baseline to Week 4, Week 8 and Week 12 for MC2-25 cream compared to MC2-25 vehicle.

Shift in frequencies of clinically significant and not clinically significant vital signs values from Baseline to Week 4, Week 8 and Week 12 for MC2-25 cream compared to MC-25 vehicle.

- Mean change in laboratory assessments (biochemistry and hematology) from Baseline to Week 4 and Week 12 for MC2-25 cream compared to MC2-25 vehicle. Shift in frequencies of normal, abnormal and abnormal clinically significant or not clinically significant laboratory values from Baseline to Week 4, Week 8 and Week 12 for MC2-25 cream

compared to MC-25 vehicle.

- Shifts in physical examination from Baseline to Week 12 by body area will be displayed. Frequencies of normal, abnormal and abnormal clinically significant and abnormal clinically not significant values of physical examination from Baseline to Week 12 for MC2-25 cream compared to MC-25 vehicle.
- Shifts in electrocardiograms (ECGs) from Baseline to Week 4 and Week 12 will be displayed. Frequencies of normal, abnormal and abnormal clinically significant and abnormal clinically not significant values from Baseline to Week 4 and Week 12 for MC2-25 cream compared to MC-25 vehicle.
- Percentage of subjects who missed 1 or more dialysis visits during the Double-blind Treatment Period as recorded on end of trial visit. Not applicable (NA) category will be presented for subjects not on dialysis.

3.6 Other Endpoints

- Skin stripping results will be provided in a separate report.

4 Analysis Populations

The analysis populations are defined as:

- Screened set (SS): all subjects who sign the informed consent form.
- Safety analysis set (SAS): all subjects who are randomized and dispensed trial medication at Randomization/Day 0, excluding subjects to whom trial medication is not dispensed or who return all the trial medication unused. Subjects will be analyzed according to the actual treatment.
- Full analysis set (FAS): all subjects who are randomized. Subjects will be analyzed according to the randomized treatment.
- Modified full analysis set (MFAS): all subjects who are randomized and returned for at least one post-baseline scheduled visit with WI-NRS data. Subjects will be analyzed according to the randomized treatment.
- Per-protocol set: (PPS): a subset of the MFAS subjects who completed the trial with WI-NRS data for Week 12 and are deemed to have no important protocol deviations that could interfere with the objectives of the trial. Important deviations of eligibility criteria and other deviations from the protocol will be assessed. Important deviations from the protocol may lead to exclusion of a subject or data points from the PPS, which could have interfered with the administration of the treatment or the evaluation of the treatment effect. A blind data review meeting will be conducted and decisions on exclusions of any subjects with important protocol deviations leading to exclusions from the per protocol set will be documented before the final trial database is unblinded.

SAS will be used for all safety analyses. FAS, MFAS, and PPS will be used for efficacy analyses.

5 Planned Analyses

5.1 Methodological Considerations

General Conventions:

- SAS[®] software (version 9.4 or higher) will be used for all data analyses and tabulations.
- Data for all investigational centers will be pooled for analysis.
- Summary tables will report data based upon the protocol scheduled time points. For patients who are withdrew early from the study, all efficacy assessments captured at the EoT visit will be assigned to the nearest protocol scheduled time point.

Counts and percentages: Categorical variables will be described by summary tables of frequencies (counts and percentages) per treatment group

Descriptive Statistics:

Descriptive summaries of continuous data will include number of non-missing values, mean, standard deviation (SD), median, minimum, maximum and 1st Quartile (Q1) and 3rd Quartile (Q3). Descriptive summaries of categorical variables will include frequencies and percentages. Missing values will not contribute to the denominator of the percentages.

Statistical tests:

Hypothesis Testing- We assume the null hypothesis is that the MC2-25 cream performs less than or equal to the MC2-25 vehicle while comparing change from baseline in WI-NRS score to Week 12.

We assume for alternate hypothesis that there is significant difference between the treatments.

The hypothesis to be tested to address the objective is:

H0: Change from baseline in mean score of weekly mean of WI-NRS to Week 12 for MC2-25 cream (δ_0) <= Change from baseline in mean score of weekly mean of WI-NRS to Week 12 for MC2-25 vehicle (δ_1)

versus

H1: Change from baseline mean score of weekly mean of WI-NRS to Week 12 for MC2-25 cream (δ_0) > Change from baseline in mean score of weekly mean of WI-NRS to Week 12 for MC2-25 vehicle (δ_1)

The primary analysis will be conducted on Mean change in weekly mean WI-NRS Score recorded in the subject's diary from Baseline to Week 12 for MC2-25 cream compared to MC2-25 vehicle and will be analyzed by a mixed model of repeated measures (MMRM).

Statistical tests will be two-sided with $\alpha = 0.05$. Superiority is concluded if a p-value of statistical hypothesis testing is below the level and the estimate of treatment difference is in favorable direction for MC2-25 cream.

Due to the phase 2 type of the trial, no adjustment due to multiple testing will be used.

No interim analyses are planned. SAS[®] software will be used for all data analyses and tabulations.

Baseline for efficacy and safety summaries is defined as the last observation prior to the first application of IMP except for weekly mean WI-NRS which is the average of at least 4 nonmissing WI-NRS values recorded in the subjects' diaries for the 7 days prior to and including the Baseline day. If there are less than 4 observations in the expected 8 days of entries, the baseline will be considered missing for weekly mean WI-NRS.

5.2 Handling of Dropouts or Missing Data

5.2.1 Missing Data

For the primary and secondary efficacy endpoints, the primary estimands using the FAS, MFAS and PPS will use a treatment policy strategy for missing data. Missing data will be replaced using a multiple imputation (MI) approach. Note, missing data includes dropouts, empty data fields after dropout date will be handled as missing data regardless of reason for drop out. MI will be performed for all populations separately only if there is a difference in populations. Seed numbers for each endpoint will use the randomly generated 4-digit numbers from the table below. Other variables that are included in the imputation model will include treatment, site, country, visit, and key baseline characteristics such as age, gender, race, CKD stage stratum⁽¹⁾ at baseline, and systemic CKD-aP treatment status⁽²⁾ at baseline. Depending on the pattern of missingness, a 2-step process may be employed. If missing data points occur for an intermediate visit, they will be imputed first using a Markov Chain Monte Carlo (MCMC) method. As a result, a monotone missingness pattern will be obtained for the data to be fully imputed. The subsequent imputation will use general regression for continuous variables and logistic regression for categorical variables under the assumption data are missing at random to produce 20 imputed datasets where the remaining missing data are filled in using 20 separate sets of values. For the categorical secondary variables, the percentages will be calculated from the above imputed data.

- (1) CKD stage stratum at baseline= A. ≥40% of subjects must be on dialysis (HD or HDF) and must be CKD stages 4-5 (CKD stage 4-5 dialysis) B. ≥20% of subjects must Not be on dialysis and must be CKD stages 4-5 (CKD stage 4-5 non-dialysis) C. ≥20% of subjects must Not be on dialysis and must be CKD stage 3 (CKD stage 3)
- (2) Systemic CKD-aP treatment status at baseline will be flagged as "Yes" if prior/concomitant medication falls within one of the ATC groups provided in Section 6.3.2

Table 9 Population and Random Seed Number

Population	Random Seed Number
FAS	6529
MFAS	7631
PPS	9376

For each copy of the imputed datasets, both the primary and secondary endpoints involving the same endpoint variable will be analyzed in the same way as described in the primary and secondary analyses in Sections 5.5.1 and 5.5.2, respectively. Results from the copies of the imputed datasets will be synthesized using SAS[®] Proc MIANALYZE.

Using the FAS for the primary endpoint analyses, a sensitivity analysis will be performed using last observation carried forward (LOCF; treatment policy). If a subject is given prohibited therapy, all missing data and data for visits after the start of prohibited therapy will use the MI approach described above in another analysis (hypothetical strategy).

If deaths occur, further estimands may be defined following a composite endpoint strategy.

There will be no imputation of missing data for the PPS which will use the data as observed following a treatment policy strategy. There will be no imputation of missing data for safety endpoints.

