6.7.2 Prohibited therapies from baseline to the end of the treatment period

Use of any therapy that would exclude the subject from participation in the trial (as specified in Section 5.3) is also prohibited during the treatment period, which includes therapies in the following categories:

- Start of new or change of existing systemic treatment for CKD-aP, including but not limited to antihistamines, corticosteroids, opioids, GABA analogues, or kappa opioid receptor agonists (but stable systemic CKD-aP treatment can be continued).
- Any topical treatment on CKD-aP areas, including but not limited to emollients, antihistamines, and corticosteroids

- Therapeutic anticoagulation treatment for subjects who have skin biopsies performed (heparin administered in association with dialysis is allowed but in such cases skin biopsies must not be performed on a dialysis day)
- Any light therapy for CKD-aP, including but not limited to UV-B
- Start of new or change of existing non-biologic systemic immunosuppressive treatment, including but not limited to corticosteroids, cyclosporin and tacrolimus
- Start of new or change of existing biologic systemic treatment, including but not limited to etanercept, adalimumab, alefacept, infliximab, and ustekinumab

If a prohibited therapy is used during the trial, treatment with the IMP shall not automatically be discontinued. After consultation with the sponsor's or designee's Medical Monitor, the investigator shall use his/her judgement to decide if (in the following prioritized order) 1) The prohibited therapy can safely be stopped; 2) the prohibited therapy cannot safely be stopped but the IMP treatment can safely continue alongside the prohibited therapy; or 3) the prohibited therapy cannot safely be stopped and the IMP treatment cannot safely continue alongside the prohibited therapy. The event must be reported as a protocol deviation.

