7.12 Adverse events

7.12.1 Adverse events assessments

The investigator or designee is responsible for obtaining, assessing, and documenting all AEs during the trial.

An AE is any untoward medical occurrence in a patient or clinical investigation subject administered an investigational or non-investigational medicinal product and which does not necessarily have to have a causal relationship with this treatment. An AE can therefore be any unfavourable and unintended sign (including an abnormal laboratory finding, for example), symptom, or disease temporally associated with the use of a medicinal product, whether or not considered related to the medicinal product.

All AEs will be documented in the eCRF, including a description of each AE, AE relationship to IMP administration, start and stop dates, seriousness, severity, action taken and outcome.

Any AE that meets the serious criteria must be reported as an SAE to PharmaLex (PLX) within 24 hours of first awareness.

Contact information:

Company: PharmaLex A/S, [name]

E-mail: [contact]

Throughout the trial, the occurrence of AEs should be monitored by nondirective questioning of the subject at each visit. Information on AEs can also be obtained from signs and symptoms detected during examinations, observations made by the trial site personnel, or spontaneous reports from subjects. Pre-existing conditions that worsen during the trial should also be recorded as AEs. This will also include worsening of the disease as judged by the investigator.

AEs requiring therapy must be treated in accordance with recognised standards of medical care to protect the health and well-being of the subject. Treatment due to an AE will be recorded in the subject's records and on the appropriate eCRF.

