8.8.1 Primary endpoint

The primary endpoint, mean change in weekly mean WI-NRS recorded in the subject's diary from Baseline to Week 12 for MC2-25 cream compared to MC2-25 vehicle, will be analysed by a mixed model of repeated measures with Baseline weekly mean WI-NRS as covariate and treatment, CKD stage stratum at baseline, systemic CKP-aP treatment status at baseline and visit as fixed factors with a two-sided α =0.05. The weekly mean WI-NRS is calculated as the average of minimum 4 WI-NRS values recorded once daily in the subject's diary from 7 days prior to and including the visit days (i.e., must be recorded for 8 days total).

On the FAS, the primary analysis and one sensitivity analysis will follow a treatment policy strategy irrespective of any potential intercurrent events. On primary analysis, missing values will be replaced following a multiple imputation procedure adequate for the endpoint assuming missingness appearing at random and based on 20 imputations. On the FAS, sensitivity analyses will include imputation by last observation carried forward (LOCF; treatment policy strategy) and multiple imputation of missing data and all data after start of rescue medication (hypothetical strategy).

Applying the same statistical model, further estimands include multiple imputation on the MFAS and as observed on the PPS, both following a treatment policy strategy. If deaths occur, further estimands may be defined following a composite endpoint strategy.

Supportive subgroup analyses will be conducted by dialysis status and CKD stages and by country on the FAS.

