5.2.3 Analysis Windows

As subjects do not always adhere to the protocol visit schedule, the following rules are applied to assign actual visits to analysis visits. Listed below are the visit windows and the target days for each visit. The reference day is Baseline, Study day 1. If a subject has 2 or more actual visits in 1 visit window, the visit closest to the target day will be used as the protocol visit for that visit window. The other additional visit(s) will not be used in the summaries or analyses, but they can be used for determination of clinically important endpoints. If 2 actual visits are equidistant from the target day within a visit window, the later visit is used.

Table 10 represents the analysis windows assigned for efficacy and safety analysis and the corresponding range of treatment days (window) during which data for a particular nominal visit will be collected. The analysis windows will be calculated from the first application of study product. These are analysis windows that contain, but are not same as, the actual visit windows.

For assessments that are not planned on Week 1, the visit window for such assessments will be starting at Week 4.

Study Week/ Period	Study Visit	Target Day	Window
Screening	Visit 1 (V1)	-28 to -1	
Baseline/ Week 0 (on site)	Visit 2 (V2)	1	1
Week 1 (on site)	Visit 3 (V3)	8 (±1)	2-19
Week 4 (on site)	Visit 5 (V5)	29 (±4)	20-43
Week 8 (on site)	Visit 7 (V7)	57 (±4)	44-71
Week 12 (on site/EoT)	Visit 9 (V9)	85 (±4)	72-92
Week 14 (FU)	Visit 10 (V10)	±2 Weeks after EoT	

Table 10Study Period, Visit and Target Day

For the hypothetical strategy, subjects given prohibited therapies will have WI-NRS data set to missing for visits after the start of the prohibited therapies and then missing data will be estimated using MIs. Subjects with an ET visit will be excluded from the PPS analyses. Safety data collected during an ET visit will remain at the Week 12/EoT visit.

Note: As per the CDISC, baseline is defined as Day 1 and not as Day 0. Therefore, there is a difference of one day between study day as defined in protocol and target day (Table 10).

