5.5.1 Primary Efficacy Analyses

The primary endpoint will be analyzed using a mixed model of repeated measures (MMRM) with baseline weekly mean WI-NRS as a covariate and treatment, CKD stage stratum at baseline, systemic CKP-aP treatment status at baseline and visit as fixed factors and subject as a random factor with a 2-sided $\alpha = 0.05$. An unstructured variance/covariance structure will be used. Least squares (LS) means and standard errors (SE) for each treatment group will be displayed along with the difference in LS means between active and vehicle with the corresponding SE, 95% confidence interval (CI) and p-value.

Descriptive summaries and listings by subject and visit will be provided.

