5.6.3 Prior and Concomitant Therapies/ Medications

Prior Therapies/ Medications:

Prior Therapies/Medications include any therapy or medication with start date prior to the start of IMP application. They will be classified according to the World Health Organization Drug Dictionary (WHO-DD; version March 2022 Q) as prior medication.

Concomitant Therapies/ Medications:

Concomitant therapies/ medication will include therapies/ medications starting before or after the start of IMP application and continuing after the start of IMP application. They will be classified according to the WHO-DD; version March 2022 Q.

Descriptive summaries will be by WHO-DD Anatomical Therapeutic Chemical (ATC) level 2 and ATC level 4. There will be separate summaries for all prior therapies/ medications, prior therapies/ medications that were ongoing at baseline, and concomitant therapies/ medications. Prior and concomitant therapies/ medications will be listed by subject.

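### The SAP's rule for systemic CKD-aP treatment status at baseline has no date condition, so read literally it lets medication started after randomisation into the primary model as a baseline factor

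*SAP*

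**What the plan says.** SAP 5.5.1 fits the primary MMRM with "systemic CKP-aP treatment status at baseline and visit as fixed factors", alongside treatment, CKD stage stratum and baseline weekly mean WI-NRS. SAP 5.5.2 uses the same factor in the GEE models, and SAP 5.2.1 puts it in the imputation model.

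The factor is defined only in footnote (2) of SAP 5.2.1. It is Yes "if prior/concomitant medication falls within one of the ATC groups provided in" Section 6.3.2. The footnote names the variable as a status at baseline but gives no start date, stop date or ongoing condition.

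SAP 5.6.3 defines the two terms that the footnote relies on. Prior medication is anything that started before the first application, whether or not it has stopped. Concomitant medication "will include therapies/ medications starting before or after the start of IMP application", provided that it continues after that point. The same section plans a separate summary of "prior therapies/ medications that were ongoing at baseline". SAP 6.1 describes a class of medication that is both prior and concomitant. The footnote refers to neither.

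The protocol expects that new systemic treatment may be started during the trial. Section 7.12.1 counts worsening of the disease as an adverse event and says "AEs requiring therapy must be treated in accordance with recognised standards of medical care". Section 6.7.2 prohibits new systemic CKD-aP treatment, but where it cannot safely be stopped it allows that "the IMP treatment can safely continue alongside the prohibited therapy". Protocol 8.8.1 keeps the later data in the primary analysis under a treatment policy strategy. For the hypothetical strategy, SAP 5.2.3 says that "subjects given prohibited therapies will have WI-NRS data set to missing for visits after the start of the prohibited therapies".

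**The concern.** A subject on no systemic antipruritic at Baseline who starts a gabapentinoid in Week 6 has a concomitant medication as SAP 5.6.3 defines it, in an ATC group listed in SAP 6.3.2. Followed literally, footnote (2) codes that subject Yes for status at baseline. The same start would then be an intercurrent event in one part of the plan and a baseline factor in another.

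Whether a subject starts an antipruritic depends on itch after randomisation. If the cream works, more vehicle than cream subjects will start. The Yes group then contains subjects who are doing badly and come disproportionately from the vehicle arm. The model attributes part of the vehicle arm's poorer result to the flag, and the treatment estimate moves toward zero.

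There are two further effects. In the hypothetical-strategy analysis, the data removed because of a start would be imputed from a flag set by that same start. The baseline table in SAP 5.3 uses the same drug list, so it could show post-baseline users as baseline users.

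**Working it through.** **1. The plan's own figure.** Protocol 8.2 gives d = 1.5, s = 2.46, two-sided 5%, 72 and 36 subjects, and power of at least 80%.

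- At 72/36: d / [s·√(1/72 + 1/36)] = 1.5 / (2.46 × 0.2041) = 2.987. Power is Φ(2.987 − 1.960) = 84.8%, or 84.1% with the noncentral t.
- After 10% dropout, at 65/32: 1.5 / (2.46 × 0.2160) = 2.824. Power is 79.8% with the noncentral t.

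The stated figure reproduces, with little reserve after dropout.

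**2. What the rule admits.**

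| Medication history | Footnote (2) with the 5.6.3 definitions | True status at baseline |
|---|---|---|
| Started before first application, ongoing | Yes | Yes |
| Started after first application | Yes (concomitant) | No |
| Stopped before Baseline | Yes (prior) | No |
| None listed | No | No |

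For the third row, Protocol 6.7 records therapies taken within 30 days before screening, and screening lasts up to 28 days: 30 + 28 = 58 days before Baseline. Exclusion 13 bars changes in the last 21 days. If a stop counts as a change, a CKD-aP drug stopped 22 to 58 days before Baseline would be coded Yes.

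**3. Size of the effect of later starts.** The documents give neither baseline use nor start rates, so everything in this step except d, s and the arm sizes is assumed.

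- Model: Week 12 ANCOVA on treatment and flag, complete data, as a stand-in for the MMRM; 20,000 simulated trials per setting.
- Correlation between Week 8 and Week 12: 0.7.
- Baseline use p: 10%, 30% or 50%, with no prognostic effect.
- Start rule: an untreated subject in either arm starts a listed drug if the Week 8 value exceeds a common threshold, which a proportion q = 10% or 20% of vehicle subjects exceed.
- Share starting: vehicle q(1 − p); cream (1 − p)[1 − Φ(z₁₋q + 1.5/2.46)]. For p = 30% and q = 20%: vehicle 0.20 × 0.70 = 14%; cream 0.70 × [1 − Φ(0.842 + 0.610)] = 0.70 × 0.073 = 5%.

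Results at 72/36 when the started drug has no effect on itch:

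| p | q | Difference, correct flag → literal flag | Power, correct → literal |
|---|---|---|---|
| 10% | 10% | 1.503 → 1.416 | 84.1% → 80.8% |
| 10% | 20% | 1.504 → 1.294 | 84.1% → 75.2% |
| 30% | 10% | 1.501 → 1.472 | 83.7% → 82.7% |
| 30% | 20% | 1.503 → 1.417 | 84.2% → 81.1% |
| 50% | 10% | 1.498 → 1.486 | 83.5% → 83.1% |
| 50% | 20% | 1.504 → 1.464 | 84.0% → 82.7% |

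- Smallest loss: 1.498 − 1.486 = 0.01 points and 0.4 power points. Largest at 72/36: 1.504 − 1.294 = 0.21 points and 8.9 power points. The largest setting repeated at 65/32 gives 79.3% → 69.9%, a loss of 9.4.
- If the started drug lowers itch by 1.5 points (p = 30%, q = 20%), the difference goes from 1.362 to 1.305 and power from 79.6% to 76.6%. The fall from 1.50 to 1.36 belongs to the treatment policy strategy; only the last 0.06 comes from the flag.
- With no true treatment difference, the estimate is 0.00 and rejection is 4.8-5.2% with either flag.

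**4. Sensitivity to the start rule.** A separate simulation at 65/32 let every untreated subject without improvement start a listed drug. With 10% baseline use (19% of vehicle and 7% of cream subjects starting), the difference falls to 1.18 and power goes from 78.9% to 68.7%. Direction is stable across rules; size is not.

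**The case against.** The strongest reply is that the time condition is already in the name. The variable is called a status at baseline wherever it appears. SAP 5.1 defines baseline as the last observation before first application, and SAP 5.3 pairs the 6.3.2 list with use at baseline. On this reading the footnote supplies the drugs and the label supplies the date. Prior/concomitant may simply name the data source, or it may mean the both-prior-and-concomitant class in SAP 6.1, which would give the correct flag. The plan also handles later starts through its estimand strategies, which argues against their being meant to redefine a baseline factor.

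Much of this stands. A reader might infer that a Week 6 starter is certain to be coded Yes. The documents do not support that, because a programmer could restrict the flag correctly. But the SAP 5.1 definition is written for efficacy and safety summaries, and the footnote does not invoke the 6.1 class or the ongoing-at-baseline category. Two programmers could therefore build different primary models from the same text.

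It is also fair that every rate behind the size is assumed, and that in an exploratory phase 2 trial attenuation is a conservative error.

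A reader might also object that the flag requires no CKD-aP indication, or that SAP 6.3.2 names no opioid or kappa opioid agonist group although exclusion 13 does. These may misclassify subjects, but they do not bias the comparison. An ATC rule without an indication is a defensible, objective choice. Whether the listed group of other analgesics covers those drugs cannot be settled from the documents.

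**Conclusion.** The point holds as a defect in an operational definition. Read with the SAP's own terms, footnote (2) does not exclude post-randomisation starts or medication already stopped, and it feeds the primary, secondary and imputation models.

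Under the assumed rates the loss is about 0.01 to 0.21 points on a planned 1.5, and about 0.4 to 9 power points. It is about 1 to 3 power points at 30% baseline use, and negligible with few starters or high baseline use. A heavier start rule gives larger losses. These figures rest on a complete-data Week 12 model and on rates that the documents do not supply.

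A reader might infer a risk of a false positive finding. The simulations do not support that: type I error stays at about 5%. The change should be made before unblinding, because the flag is a prespecified primary covariate and planned power after dropout is only about 80%.

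**What to change.** Rewrite footnote (2) of SAP 5.2.1: the flag is Yes only if a medication in a group listed in Section 6.3.2 started before, and was ongoing at, the first IMP application. Add that a later start never changes the flag and is handled only by the treatment policy strategy in the primary analysis and by the planned hypothetical-strategy analysis. Use the same flag for the baseline table in SAP 5.3.

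Optionally, check under blind whether the 6.3.2 list covers the opioids and kappa opioid agonists named in exclusion 13. No indication condition is needed.

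The cost is one SAP sentence and one programming condition before unblinding. Protocol 6.7 already collects start and discontinuation dates, so there are no new data or visits and no loss of power.
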